# 14.1 Sample Size

100 ADHD adolescents will be enrolled in the study, randomised into the fMRI-NF of rIFC (N = 50) and the sham NF (N = 50).

The estimates of a clinically relevant effect size were calculated from our IOPPN pilot study on fMRI-NF in ADHD adolescents using the exact same outcome measures. ES for clinical efficacy in our pilot study was around 0.6. For a mean ES of 0.6 and a power of 80% with a p < 0.05, we would need 45 children in each group. We hence powered the study to include 50 children in each group accounting for a generously estimated potential drop-out rate of up to 10%. Our pilot study was well tolerated by ADHD children who liked the Neurofeedback "game" and we had a drop-out rate of only 5%, which is lower than the 6-10% drop-out rate we have had for studies of repeated fMRI scans under several medication conditions.

# 14.2 Randomisation

The ADHD children (non-medicated or on stable medication) will be randomized to sham or real fMRI-NF of rIFC, 50 in each group. Stratification factors will include medication status (non-medicated/stable) and age. Patients will be randomly assigned in a 1:1 ratio with varying block size to either the experimental (real fMRI-NF) or the control (sham-fMRI-NF) groups. This assignment will be realized by a computer-generated, web-based tool provided by the Clinical Trials Unit of the IOPPN, KCL.

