ADHD affects 5-10% of school aged children in the UK. ADHD causes symptoms such as difficulty in focussing attention, impulsiveness and hyperactivity and can seriously impact life, both at home and at school. Underlying their impulsiveness, children with ADHD have problems with self-control, timing and attention. Over the last two decades of brain imaging we and others have shown that these cognitive problems are due to reduced activity in the right inferior frontal part of the brain. Furthermore, one of the main mechanisms of action of stimulant medication, which works in 70% of the cases, is to increase the activity of this brain region. We argue that a therapy that is based on the neuroscience of ADHD, i.e. on the main brain abnormality in ADHD and on the main mechanism of action of stimulant medication, but without side effects, is likely to be successful. We therefore aim to train patients to self-regulate this region of their brain which is underfunctioning, by providing them feedback of their own brain activity.

Patients can be treated by self-regulation of the underlying pathological networks directly, through Neurofeedback (NF). It has been shown that modulating brain function via NF can change behaviour and improve cognitive functions (Birbaumer, et al., 2009). NF is an operant conditioning procedure that allows subjects to achieve volitional and conscious self-control over otherwise unconscious brain activation (and associated processes) mainly through real-time audio/visual feedback. This is achieved by continuously updating subjects with representations of their brain activity on a PC and training them to modulate these representations, usually through trial and error. Changes in the desired direction are rewarded. Since NF can be run as a computer game it is attractive to children. Given that Neurofeedback teaches participants self-regulation of their brain and ADHD is typified by poor self-control, it is the psychiatric disorder where NF has been most applied, using electrophysiology Neurofeedback (EEG-NF).

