# 14. Statistics

Behavioral data and fMRI analysis will be conducted using statistical techniques with a primary focus on repeated measures ANOVAs (within-subject factor TIME; between subject factor GROUP). Supplementary analyses may include parametric correlation analyses (for example Pearson's correlation tests).

The named researchers have substantial and proven experience in these types of analyses, having published and taught extensively.

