#### 14.3 Analysis

A description of the statistical methods to be employed, including timing of any planned interim analyses should also be provided The level of significance that is to be used in each trial analysis must be stipulated, together with the procedure(s) for accounting for any missing, unused, and spurious data. Procedures for reporting any deviation from the original statistical plan should be described and justified. The data set for any analysis must be clearly stipulated (e.g. "all subjects", "randomised subjects", "intent to treat") and the population(s) should be clearly defined. Define the trial stopping rules if appropriate.

For all analyses, repeated measures ANOVAs will be conducted with TIME as within-subject factor and GROUP as between subject factor. Supplementary analyses may include parametric correlation analyses (for example Pearson's correlation tests).

The named researchers have substantial and proven experience in these types of analyses, having published and taught extensively.

For missing data, imputations will be used. The individual estimates from the multiply-imputed datasets will then be used to calculate a combined estimate by applying Rubin's Rules [Little and Rubin, 2002].

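### The stated model omits the stratification factors, so between-arm tests forgo precision if medication status or age predicts change

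*Protocol*

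**What the plan says.** Randomisation is 1:1 in blocks of varying size, and section 14.2 names two factors: "Stratification factors will include medication status (non-medicated/stable) and age". Sections 8.1, 10.4 and 11 give the same two factors. No age cut-point is stated.

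The analysis is described twice. Section 14 puts a "primary focus on repeated measures ANOVAs (within-subject factor TIME; between subject factor GROUP" and section 14.3 is broader: "For all analyses, repeated measures ANOVAs will be conducted with TIME as within-subject factor and GROUP as between subject factor". Neither section names medication status or age as a factor or covariate. The only supplementary analyses mentioned are parametric correlations.

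Section 14.1 sizes the trial on the pilot: "ES for clinical efficacy in our pilot study was around 0.6". It continues "For a mean ES of 0.6 and a power of 80% with a p < 0.05", "we would need 45 children in each group", and raises this to 50 per group for up to 10% drop-out.

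**The concern.** Stratified blocks remove most of the chance difference between arms that is due to the strata. A model without the strata still counts that variation as error. If the strata predict the quantity being tested, the reported standard error is larger than the true one, confidence intervals are too wide and the real type I error is below 5%.

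The protocol gives some reason to expect that the factors matter. The background says that "one of the main mechanisms of action of stimulant medication, which works in 70% of the cases, is to increase the activity" of the target region, and ages run from 10 to 18. Under section 8.6, stopping stimulants before the pre, post and follow-up assessments is optional, and nothing there requires a child to be in the same state each time. A switch between assessments would enter the change score of medicated children only. The request for an unchanged regime covers only the two training weeks, so it does not protect the 6-month outcomes.

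At stake is precision on ADHD-RS and the secondary between-arm outcomes. Bias and false positives are not at stake.

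**Working it through.** **Inputs from section 14.1:** effect size d = 0.6, power 80%, p < 0.05 (taken as two-sided), 45 per group analysed.

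**Assumptions:** d is in units of the change-score SD. R² is the share of change-score variance explained by medication status and age together. The protocol gives no value, so R² is varied from 0 to 0.30.

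**1. The plan's own figure.** The normal approximation gives n = 2(1.96 + 0.84)² / 0.6² ≈ 43.6, so 44 per group. The exact t calculation gives 79.5% power at 44 and 80.4% at 45, so 45 per group. Then 45 / 0.90 = 50. The plan's numbers reproduce. A one-sided test would need only 35. The calculation counts on no gain from covariates.

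**2. What the stated model tests.** With one pre and one post measure, the GROUP x TIME test is the same as a two-sample t-test on post minus pre. Anything that shifts a child equally at both times cancels, so only an association with change matters.

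**3. Effect of leaving the strata out.** Scale the change-score SD to 1 and take the arms as balanced within strata.

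- SE reported by the unadjusted model: √(2/45) = 0.211.
- True SE: √((1 − R²) × 2/45).
- Overstatement: 1/√(1 − R²) − 1.
- Unadjusted type I error ≈ 2[1 − Φ(c/√(1 − R²))], with c the t critical value on 88 df (about 1.99).
- Unadjusted power ≈ Φ((0.6 − 0.211c) / true SE).
- Adjusted power: noncentral t with effect 0.6/√(1 − R²) on 86 df.

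For R² = 0.20, the true SE is 0.211 × √0.80 ≈ 0.189, and the overstatement is 1/√0.80 − 1 = 11.8%.

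| R² | SE overstated | Type I error, unadjusted | Power, unadjusted | Power, adjusted |
|---|---|---|---|---|
| 0 | 0% | 5% | 80.4% | 80.4% |
| 0.05 | 2.6% | 4.2% | 81.1% | 82.3% |
| 0.10 | 5.4% | 3.6% | 81.7% | 84.3% |
| 0.20 | 11.8% | 2.6% | 83.2% | 88.2% |
| 0.30 | 19.5% | 1.8% | 84.8% | 92.0% |

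The first row gives the exact t values. The type I approximation runs slightly low: it returns 4.7% at R² = 0, where the true value is 5%.

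**4. Simulation check.** 90 analysed, four strata (medication by a two-level age split), blocks of 2 and 4, 6,000 runs per scenario.

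- *Factors shift level only:* model SE 0.210 and empirical SE 0.210; power 81.0% unadjusted and 80.9% adjusted; type I error 4.9% in both.
- *R² = 0.10 on change:* type I error 4.5% unadjusted; power 80.8% unadjusted and 83.7% adjusted.
- *R² = 0.20 on change:* model SE 0.210 against a true 0.188; type I error 2.8% unadjusted; power 82.5% unadjusted and 88.4% adjusted.

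The simulation shows the same pattern. It is slightly less conservative than the formula, as expected when the last block in a stratum is incomplete.

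**The case against.** The strongest answer is that the within-child design already does most of the work. Stable effects of age or medication cancel in GROUP x TIME. The background statement about stimulants concerns the level of activity, not change over two weeks of training, and the width of the age range is also mainly an argument about level. The regime is meant to stay unchanged during training. All of this stands, and it is why the consequence is conditional.

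A reader might infer that the trial certainly loses power, or falls short of its target. The documents do not support that. The 45 per group assumes no covariate gain, and unadjusted power is at or above 80% in every scenario above. A reader might also infer that both primary endpoints are affected. The second one in section 7.1.1 is a rising trend within the active group. As worded it is not a comparison of randomised arms, so stratified allocation cannot distort a between-arm standard error for it.

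It can also be said that covariates are commonly left to the analysis plan, which is not at hand. This carries some weight, because section 14 speaks only of a main focus and neither section excludes covariates. But 14.3 names a two-factor model and applies it to all analyses. That is a stated model rather than silence, and an analysis plan that added the strata would depart from it.

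**Conclusion.** The mismatch holds: allocation is stratified by medication status and age, and the model stated for all analyses contains neither. The consequence is limited to the between-arm comparisons and depends on whether the factors predict change. If they explain 5% to 30% of change-score variance, the standard error is overstated by about 3% to 20% and about 1 to 7 percentage points of power are forgone (82.3 − 81.1 = 1.2; 92.0 − 84.8 = 7.2). If they explain none, nothing is lost.

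The error is conservative: there is no bias and no inflation of type I error, and the planned power holds. The sizes rest on the assumed R², on d being in change-score SD units, on 45 analysed per group and on a single pre-post contrast. The point is worth acting on because the remedy is nearly free and settles the covariates before the data are seen.

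**What to change.** In section 14.3, add medication status as randomised and age to the models for ADHD-RS and the secondary between-arm outcomes. If the repeated measures ANOVA is kept, include each factor's interaction with TIME, because main effects alone leave the GROUP x TIME test unchanged. Equivalently, enter both as covariates in a model of change, or of the post score adjusted for baseline. State how age enters, for example as a continuous term or in the bands used for randomisation.

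The cost is wording, plus two degrees of freedom per post-baseline contrast if age is one term. With baseline, post and 6-month measures in one model, the TIME interactions take 2 × 2 = 4 parameters on top of the two main effects. Both variables are known before randomisation. If neither factor predicts change, the power loss is negligible (80.9% against 81.0% in the simulation).

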#### 14.3 Analysis

A description of the statistical methods to be employed, including timing of any planned interim analyses should also be provided The level of significance that is to be used in each trial analysis must be stipulated, together with the procedure(s) for accounting for any missing, unused, and spurious data. Procedures for reporting any deviation from the original statistical plan should be described and justified. The data set for any analysis must be clearly stipulated (e.g. "all subjects", "randomised subjects", "intent to treat") and the population(s) should be clearly defined. Define the trial stopping rules if appropriate.

For all analyses, repeated measures ANOVAs will be conducted with TIME as within-subject factor and GROUP as between subject factor. Supplementary analyses may include parametric correlation analyses (for example Pearson's correlation tests).

The named researchers have substantial and proven experience in these types of analyses, having published and taught extensively.

For missing data, imputations will be used. The individual estimates from the multiply-imputed datasets will then be used to calculate a combined estimate by applying Rubin's Rules [Little and Rubin, 2002].

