#### 7.1.1 Primary endpoints

1) ADHD symptoms as measured on the ADHD-Rating Scale (ADHD-RS). (Dupaul et al. 1999).

2) Monotonic increase in inferior frontal lobe activation across the 14 neurofeedback sessions in the active group.

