# 7.1.2 Secondary endpoints

- 1) The ADHD Index of the Conners Parent Rating Scales (CPRS).
- 2) Stop fMRI task performance and related brain activation.
- 3) A cognitive task battery we have developed for ADHD that measures key functions including inhibition, attention, timing and motivation and which lasts 30min (Rubia, Smith, & Taylor, 2007).
- 4) Other clinical measures:
  - a. the Affective Reactivity index (ARI) (Stringaris et al., 2012) (2min)

- b. the Columbia Impairment Scale (CIS) (Bird, et al., 1003) (5min)
- c. The Mind excessive wandering scale (MEWS) (Mowlem et al., 2016)
- 4) Side effect scale (Hill & Taylor, 2001). (5min)

5) Long-term effects will be assessed 6 months after training in the primary outcome measure (ADHD-RS for parent-ratings), the ARI, the MEWS and in the performance on the cognitive task battery.

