#### 12.3 Procedures for Assessing Efficacy Parameters

The efficacy measures are parent rated behaviour scales for ADHD behaviours which will be filled in by the parents before and after the treatment and at follow-up assessment.

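### The ADHD-RS is to be tested by a TIME and GROUP repeated-measures ANOVA with no baseline covariate and no named primary contrast; a baseline-adjusted comparison at post-treatment is more precise and costs only wording

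*Protocol*

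**What the plan says.** Protocol section 14.3 fixes one model for every outcome: "For all analyses, repeated measures ANOVAs will be conducted with TIME as within-subject factor and GROUP as between subject factor". The opening of section 14 names the same model as the main approach. Neither place mentions a baseline covariate, lists the levels of TIME, or says whether the interaction or another term is the test of treatment.

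The ADHD-RS is a primary endpoint (section 7.1.1) and the primary efficacy measure (sections 12 and 12.1), but no time point is attached to it. Section 12.3 says the parent scales are "filled in by the parents before and after the treatment and at follow-up assessment", so there are three ratings. Section 7.1.2 puts the last of these among the secondary endpoints: "Long-term effects will be assessed 6 months after training in the primary outcome measure".

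Section 14.1 bases the sample size on the pilot: "ES for clinical efficacy in our pilot study was around 0.6". With "a power of 80% with a p < 0.05" it arrives at 45 children per group, raised to 50 for up to 10% drop-out. The SD by which 0.6 was standardised is not given. Randomisation is 1:1, stratified by medication status and age (sections 10.4 and 14.2).

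**The concern.** Two features of the fixed model matter for the primary question, which is whether active neurofeedback lowers ADHD-RS more than sham.

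The first is precision. With one pre and one post rating, the TIME by GROUP interaction is algebraically a two-sample t-test on change scores. It gives the baseline a fixed weight of one, where ANCOVA estimates the weight from the data. In a randomised trial both are unbiased, but the change-score test has the larger variance whenever rho is below 1. Baseline ADHD-RS is collected anyway, so the loss is avoidable.

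The second is the contrast. Because the 6-month ADHD-RS is listed as secondary, the primary effect is by implication the one just after training. The text does not say so, and it does not say whether the 6-month rating enters the primary ANOVA. If it does, the interaction tests two differences jointly, and a significant result does not show at which visit the groups differ.

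**Working it through.** **Inputs.** From section 14.1: standardised effect 0.6, power 80%, alpha 0.05, 45 evaluable per group, drop-out 10%. Assumed: rho of 0.3 to 0.7, because the protocol gives no pre-post correlation; equal SDs at the visits; complete data. Alpha is taken as two-sided, because a one-sided test would need only 35 per group.

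**1. The protocol's own figure.** n = 2(1.96 + 0.842)² / 0.6² = 2 × 7.85 / 0.36 = 43.6, so 44 per group by the normal approximation. The noncentral t needs 45 (power 80.4%). Then 45 / 0.90 = 50. The stated figures reproduce as a plain two-group comparison, with neither a repeated-measures nor a baseline term.

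**2. Two visits: interaction against ANCOVA.** In units of the post-score variance:
- change score (the interaction): 2(1 − rho)
- ANCOVA: 1 − rho²
- ratio: 2(1 − rho) / (1 − rho²) = 2 / (1 + rho)

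Taking 0.6 in post-score SD units, the effective standardised difference is 0.6/√[2(1 − rho)] for the interaction and 0.6/√(1 − rho²) for ANCOVA. Power is from the noncentral t at 45 per group; n for 80% power is by the normal approximation.

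| rho | variance ratio | effective d, interaction | effective d, ANCOVA | power, interaction | power, ANCOVA | n per group for 80%, interaction / ANCOVA |
|---|---|---|---|---|---|---|
| 0.3 | 1.54 | 0.507 | 0.629 | 66% | 84% | 62 / 40 |
| 0.5 | 1.33 | 0.600 | 0.693 | 80% | 90% | 44 / 33 |
| 0.7 | 1.18 | 0.775 | 0.840 | 95% | 98% | 27 / 23 |

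**3. The other reading of 0.6.** If 0.6 is in change-score SD units, the interaction has the stated power of about 80% at 45 per group whatever rho is. ANCOVA then needs 43.6 × (1 + rho)/2 per group: 28.3, 32.7 and 37.1, so 29, 33 and 38 at rho 0.3, 0.5 and 0.7.

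**4. Three visits in TIME.** Under compound symmetry the 2-df interaction has noncentrality (n/2) × Σ(d_t − d̄)² / (1 − rho), where d_t is the group difference at visit t, with 2 and 2 × 88 = 176 degrees of freedom. With n = 45, rho = 0.5 and differences in post-score SD units at baseline, post and 6 months:

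| differences | Σ(d_t − d̄)² | noncentrality | probability of significance |
|---|---|---|---|
| 0, 0.6, 0.6 (effect persists) | 0.24 | 22.5 × 0.24 / 0.5 = 10.8 | 84% |
| 0, 0.6, 0.3 (effect halves) | 0.18 | 22.5 × 0.18 / 0.5 = 8.1 | 72% |
| 0, 0, 0.6 (6 months only) | 0.24 | 10.8 | 84% |

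ANCOVA at the post visit has 90% power in the first two rows, because it does not depend on the 6-month result. In the third row there is no post-treatment difference to find, yet the omnibus test is significant as often as when the effect is present at both visits.

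**The case against.** The strongest reply is that nothing here is invalid. With 1:1 randomisation the two-visit interaction is unbiased and keeps its type I error. It departs from the ANCOVA answer through chance baseline imbalance, which averages out over randomisations. That stands: the two-visit point is about efficiency only.

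A reader might infer from the 66% figure that the trial is underpowered. The protocol does not support that. The figure needs both a low rho and 0.6 in post-score SD units, and section 14.1 gives neither. Section 6 says the pilot had no sham arm, so its effect size may well come from pre-post change; on that scale the planned test has about the stated power. At rho 0.7 the gain from ANCOVA is about 2 points on either account of what matters clinically.

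A reader might also infer that the protocol prescribes a 2-df test. It does not: the levels of TIME are not listed, and the separate secondary listing of the 6-month rating fits a pre/post primary analysis, in which the contrast is clear. Nor does a third visit always cost power. If the effect persists, the omnibus test has 84% at rho 0.5, against 80% for the two-visit interaction.

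Finally, it is tempting to say that the planned pooling, with estimates "used to calculate a combined estimate by applying Rubin's Rules", cannot work for such an ANOVA. It can. A two-visit interaction is one estimate with one standard error, single contrasts from three visits pool in the same way, and pooling rules exist for multi-parameter tests.

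An SAP could name the contrast. What remains is that section 14.3 fixes the model for all analyses, so an SAP using baseline adjustment would have to depart from the protocol.

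**Conclusion.** The point holds as an avoidable loss of precision together with an unnamed primary contrast, and merits a should-fix. The variance penalty of 2/(1+rho) applies for any rho below 1, given equal SDs at the two visits. Its cost in power ranges from about 18 points at rho 0.3 to about 2 at rho 0.7 if 0.6 is in post-score SD units. On the change-score scale it shows instead as 29 to 38 children per group being enough where 45 are planned. The loss of a clear post-treatment contrast is conditional on the 6-month visit entering TIME, which the protocol neither states nor rules out; the 84%, 72% and 84% figures also assume rho 0.5 and compound symmetry.

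**What to change.** In sections 14 and 14.3, define the primary ADHD-RS analysis as the active-minus-sham difference in post-treatment score, from a linear model with group, baseline ADHD-RS and the stratification factors (age, medication status). State that the 6-month difference is a separate secondary contrast. Use the same form for the other outcomes measured before and after training, each adjusted for its own baseline.

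If a mixed model over the post and 6-month visits is preferred, include visit-by-group and visit-by-baseline terms and an unstructured covariance. Without these it does not in general match ANCOVA at the post visit.

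The cost is wording in two sections. Baseline scores and stratification factors are already collected, and no extra visit or participant is needed. The change should be made before any unblinded data are seen.
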